9 RESEARCH METHODS

9.1 Registry Design

This is a multicentre, global, prospective, non-interventional, observational, open-ended, post-authorisation safety surveillance registry designed to collect safety and effectiveness data on the use of Increlex® in children and adolescents with SPIGFD. Data on treatment exposure, compliance and QoL of participants will also be collected.

The objective is to screen all Increlex®-treated patients with SPIGFD at each participating site of the participating countries with the aim of enrolling as many patients as possible.

The decision to prescribe Increlex® will be made prior to and independently of the decision to enrol the patient in the registry. Treatment with Increlex® should be directed by physicians who are experienced in the diagnosis and management of patients with growth disorders. The dose should be individualised for each participant according to the locally approved product information. The data collected for a participant will be those that exist in their medical records as part of standard medical care except for additional QoL assessments and post-treatment safety follow-up in the context of fulfilling the Specific Obligation (SO2). Data will be collected utilising an electronic Case Report Form (eCRF) via the internet.

The date of the inclusion visit is not determined by the protocol. Patients who have started Increlex® treatment before the implementation of the registry in their country may also be enrolled. Data will be then retrospectively collected in the eCRF.

During the first visit, the Investigator will check the patient's eligibility according to the inclusion and exclusion criteria and must obtain written informed consent before any further data collection.

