9.2.1 Inclusion Criteria

(2) Children and adolescents from 2 to 18 years:

- For US, patients starting or planning to start or currently receiving treatment with Increlex® therapy for severe primary IGF-1 deficiency as defined by the US Increlex® prescribing information or for growth hormone (GH) gene deletion who have developed neutralizing antibodies to GH.
- For EU, patients starting or planning to start or currently receiving treatment with Increlex® therapy according to the locally approved product information. Note:

not applicable for patients enrolled in the EU-IGFD registry and entering or currently in the post-treatment period.

(2) Signed informed consent as per local regulations needs to be obtained. Parents or legally authorised representatives if applicable must give signed informed consent before any registry-related activities are conducted. Assent from the participant should also be obtained as appropriate.

9.2.2 *Exclusion Criteria*

(1) Patient currently participating in an Increlex® clinical trial.

(2) Patient currently participating in any clinical trial for growth retardation.

(3) Patient with any contraindication to Increlex® or any condition subject to special warning as per the locally approved label.

- For US patients, these include patients with hypersensitivity to the active substance or any of the excipients, patients with active or suspected neoplasia and patients with closed epiphyses.
- For EU patients: these include patients with hypersensitivity to the active substance or any of the excipients, patients with active or suspected neoplasia or any condition or medical history which increases the risk of benign or malignant neoplasia and patients with closed epiphyses. Note: not applicable for patients enrolled in the EU-IGFD registry and entering or currently in the post-treatment period.

Note: for any patients enrolled in the registry under previous inclusion/exclusion criteria (i.e. before implementation of Protocol Amendment #6), who would be ineligible according to any of the above inclusion or exclusion criteria, e.g. receiving Increlex® for an indication not covered by the locally approved product information, a letter will be sent to the Investigator to alert him/her about the off-label use of the product (specifically for the risk of neoplasias). The patient could continue to be followed up in the registry for safety data in the post-treatment period.

9.2.3 *Registry Population*

9.2.3.1 *Physician Profile*

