Eligible Investigators for the global registry will be:

- Physicians who are experienced in the diagnosis and management of children and adolescents with SPIGFD;
- Physicians located in a country where Increlex® is approved and marketed and where the study is implemented;
- Physicians who have prescribed/plan to prescribe Increlex® according to the locally approved product information.

9.2.3.2 *Participant Population*

Eligible participants will be children and adolescents from 2 to 18 years starting or planning to start or currently receiving treatment with Increlex® therapy for SPIGFD according to the locally approved product information in participating countries. In order to be enrolled, participants must comply with all the inclusion criteria (Section 9.2.1) and exclusion criteria (Section 9.2.2).

9.2.3.3 *Patient Screening and Number of Participants*

The current global Increlex® registry should be proposed to all eligible Increlex®-treated patients at the site.

During screening, Investigators must explain the purpose of the registry as well as the identified risk of neoplasia and the need to be followed up until at least 5 years after the end of treatment. Investigators must give the Participant Information Sheet (PIS) to the participant (and/or the participant's parents or legally authorised representative) which summarises all information related to the study given by Investigators:

- If participation in the registry is confirmed (the participant/parents or legally authorised representative agree to participation), the informed consent will be discussed and signed (before any related data collection) and the enrolment visit will be recorded.
- If the patient is not participating in the registry, registration date and reason for non-participation should be recorded in the eCRF in order to assess the proportion of non-included patients, only if the patient has no objection to this data collection.

A unique number will be attributed to each participant enrolled, to be used throughout the registry.

9.2.4 *Registry Duration*

9.2.4.1 *Recruitment Period*

This is an ongoing open-ended registry. Enrolment in the EU-IGFD registry started in December 2008.

For each new participating site/country, enrolment will start following local site initiation with all necessary regulatory and ethics local approvals.

9.2.4.2 *Treatment Duration*

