- Description and evolution of QoL in participants aged 4 and over using EQ-5D version EQ-5D-Y including changes from baseline at year one, at end of treatment and at FAH;
- Description of neoplasia (benign and malignant) and hypoglycaemia according to the timeframe of occurrence (e.g. within the first 3 years after start of treatment, between 3 and 5 years and over 5 years).

9.3.2 *Variables*

9.3.2.1 *Demographic and Baseline Variables*

The registry will collect the following data:

- Demographic data on children and adolescents receiving Increlex® treatment: sex, date of birth (month and year), birth weight and length, gestational age, previous and current height, sitting height and weight;
- Parental heights (biological relatives only);
- Baseline height, sitting height, weight, bone age and method, echocardiogram, funduscopy and pubertal (Tanner) stage;
- Pregnancy status;
- PAH;
- Diagnosis of SPIGFD (documented by height SDS; IGF-1 levels and IGF-1 SDS; GH levels), date of diagnosis and associated aetiologies, and date of growth failure (short stature) diagnosis, if different from SPIGFD diagnosis date;
- IGF-1 generation test results and IGF-1/IGFBP3 concentrations;
- GH concentrations including basal/random and highest stimulated;
- Serum IGFBP3;
- GHBP;
- Genetic test results and date of genetic testing;
- Current and previous illnesses including congenital conditions and neoplasia;
- Previous and concomitant medications;
- Personal and family history of neoplasia;
- Prior growth-promoting therapies: GH, IGF-1, steroid hormones such as sex steroids (testosterone and oestradiol);
- Baseline QoL assessment using EQ-5D version EQ-5D-Y.

9.3.2.2 *Safety Variables (Primary Analyses; Treatment Period and Secondary Analyses; Treatment and Post-treatment Follow-up Periods)*

Data on the following safety variables will be collected from enrolment to the end of the post-treatment follow-up period:

- For all AEs, irrespective of causality, including SAEs, AESI and targeted AEs, start/end date, time to onset, nature, severity, seriousness, causality assessment, any treatment administered for the AE, action taken and outcome;
- Deaths, irrespective of causality, including date and cause of death;
- Special situations, irrespective of causality, including start/end date, category, description, whether the special situation led to an AE and outcome;
- Concomitant medications including concomitant treatment with GH, with start/end dates;

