- Echocardiography and funduscopy results.

9.3.2.3 *Effectiveness Variables (Secondary Analyses; Treatment and Post-treatment Follow-up Periods)*

Data on the following effectiveness variables will be collected at enrolment, during treatment and after the end of treatment:

- Height and sitting height;
- Weight;
- Pubertal (Tanner) stage: pubic hair, testicular volume, breast development;
- Bone age;
- IGF-1 concentrations;
- IGFBP3 (treatment period only);
- FAH.

9.3.2.4 *Treatment Variables (Secondary Analyses; Treatment Period)*

Data on the following treatment variables will be collected from start to end of treatment:

- Dose of Increlex® at the start of treatment (mg/kg or mcg/kg), mode of administration and date of first Increlex® intake;
- Any dose adjustments and dose interruptions (including adjusted dose and dates) throughout the study including reasons for adjustment;
- Dose of Increlex® at the end of treatment (mg/kg or mcg/kg) and date of last Increlex® intake;
- Reason for discontinuing therapy (most appropriate response): attained adult height, AE, lost to follow-up, noncompliance, participant/parent/legally authorised representative decision, financial/insurance, changed physician, lack of effectiveness, shortage of Increlex®, COVID-19 or other.

9.3.2.5 *Quality of Life Variables (Secondary Analyses; Treatment and Post-treatment Follow-up Periods)*

Data for the following QoL assessments will be collected at baseline (start of treatment), at year one, at end of treatment and at FAH:

- Changes in QoL assessment using EQ-5D version EQ-5D-Y.

The QoL of participants will be assessed using the EQ-5D-Y paediatric questionnaire, a child-friendly standardised measure of health status developed by the EuroQol Group, denoted 'Youth' as being adequate for both children and adolescents [24].

The EQ-5D-Y consists of two pages, a descriptive system and a visual analogue scale (VAS). The descriptive system comprises five dimensions, using child-friendly wording: mobility; looking after myself; doing usual activities; having pain or discomfort; feeling worried, sad or unhappy. Each dimension has three levels: no problems/no pain/not worried, some problems/some pain/a bit worried, a lot of problems/a lot of pain/very worried, from which the respondent chooses the most appropriate. The EQ VAS records the respondent's self-rated health on a 0-100 vertical VAS from 'The best health you can imagine' to 'The worst health you can imagine'.

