All treatment emergent AEs (TEAEs) will be coded according to MedDRA and will be classified by MedDRA primary system organ class (SOC) and preferred term (PT). The incidence of all TEAEs, SAEs, AESI, targeted AEs, AEs leading to death and AEs leading to withdrawal will be tabulated by primary SOC and PT. In addition, summary tables by maximum intensity and drug relationship will be presented.

AE listings will be presented by participant, primary SOC and PT.

The relationship of frequently occurring AEs, e.g. hypoglycaemia, to prognostic variables such as age, pubertal status, and dose will be explored.

All primary safety data will also be included in the participant data listings.

9.7.2.6 *Secondary Analyses*

Safety Analyses

The secondary safety analyses will be based on the Safety Population. Adverse event data are from the post-treatment period only but data on special situations and concomitant medications are from the treatment and post-treatment periods.

An overall summary table of AEs occurring during the post-treatment period (over 30 days after the last dose) including SAEs, AESI, targeted AEs, all AEs and AEs leading to death will be presented with the number and proportion of participants and the number of events.

The incidence of all post-treatment AEs, SAEs, AESI, targeted AEs and AEs leading to death will be tabulated by MedDRA primary SOC and PT. In addition, summary tables by maximum intensity and drug relationship will be presented.

The same analyses will be performed in a subset of children and adolescents exposed to Increlex® for at least 3 years.

Post-treatment AE listings will be presented by participant, primary SOC and PT.

An overall summary table of special situations occurring during the treatment and post-treatment periods will be presented with the number and proportion of participants and the number of events. For the post-treatment period, the same analyses will be performed in a subset of children and adolescents exposed to Increlex® for at least 3 years.

Concomitant medications during the treatment and post-treatment periods will be tabulated.

Incidence of neoplasia (benign and malignant) and hypoglycaemia will be presented according to the timeframe of occurrence (e.g. within the first 3 years after start of treatment, between 3 and 5 years and over 5 years).

All secondary safety data will also be included in the participant data listings.

Effectiveness Analyses

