11.2 Collection and Reporting of AEs, SAEs and Special Situations

11.2.1 *Collection of the AEs/SAEs/Special Situations in the eCRF*

The collection and reporting of AEs will follow regulations related to non-interventional studies.

All AEs, whether they are serious/nonserious, related/unrelated, and all special situations should be collected in the eCRF during the course of the study. Adverse events will be assessed according to incidence, intensity, causality, outcome, action taken and seriousness.

All AEs will be collected in the eCRF from the signing of the ICF until the end of the long-term post-treatment follow-up.

The method of recording, evaluating, and assessing causality of AEs and SAEs and the procedures for completing and transmitting SAE/related AE reports are provided below.

Care will be taken not to introduce bias when detecting AEs and/or SAEs. Open-ended and non-leading verbal questioning of the participant is the preferred method to inquire about AE occurrences.

AE and SAE Recording

- When an AE/SAE occurs, it is the responsibility of the Investigator to review all documentation (e.g. hospital progress notes, laboratory reports, and diagnostics reports) related to the event.
- The Investigator will then record all relevant AE/SAE information in the eCRF.
- It is not acceptable for the Investigator to send photocopies of the participant's medical records to the Sponsor in lieu of completion of the AE/SAE CRF page.
- There may be instances when copies of medical records for certain cases are requested by the Sponsor. In this case, all participant identifiers, with the exception of the participant number, will be redacted on the copies of the medical records before submission to the Sponsor.
- The Investigator will attempt to establish a diagnosis of the event based on signs, symptoms, and/or other clinical information. Whenever possible, the diagnosis (not the individual signs/symptoms) will be documented as the AE/SAE.

11.2.2 *Reporting of SAEs, Nonserious Adverse Drug Reactions and Special Situations to Sponsor Pharmacovigilance*

Investigators must report to the Sponsor's Pharmacovigilance contact all the following events using the Adverse Drug Reaction Form [REDACTED]

- All SAEs/AESI/targeted AEs – related and non-related;
- All related nonserious AEs (Adverse Drug Reactions (ADRs));
- Any special situations (see definitions in Section 11.1.2).

Primary Data Collection Noninterventional Studies (NIS)

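### Patients already on Increlex can enrol, but adverse events are captured only from consent while incidence is banded from first dose, so early-band incidence will be too low unless delayed entry is handled

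*Protocol*

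**What the plan says.** **Entry.** Section 9.1 leaves the inclusion date open: "Patients who have started Increlex® treatment before the implementation of the registry in their country may also be enrolled". The next sentence adds: "Data will be then retrospectively collected in the eCRF". Section 9.2.3.2 admits children "starting or planning to start or currently receiving treatment with Increlex® therapy for SPIGFD". A newly recruited patient who has already stopped treatment does not fit that description.

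**Event capture.** Section 9.3.2.2: "Data on the following safety variables will be collected from enrolment to the end of the post-treatment follow-up period". Section 11.2.1: "All AEs will be collected in the eCRF from the signing of the ICF until the end of the long-term post-treatment follow-up". In Table 1 the adverse event row is marked at follow-up and post-treatment visits but not at enrolment. Section 9.2.7.1 records earlier hypoglycaemia and neoplasia as medical history. Exposure follows a different clock (section 9.3.2.4): "Data on the following treatment variables will be collected from start to end of treatment".

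**Selection on neoplasia.** Section 9.2.2 excludes US "patients with active or suspected neoplasia and patients with closed epiphyses". The EU list also excludes a history that raises neoplasia risk. Section 9.2.9 has treatment stopped when neoplasia develops, with an exception for US patients with a benign neoplasm.

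**Analysis.** Section 9.7.2.6: "Incidence of neoplasia (benign and malignant) and hypoglycaemia will be presented according to the timeframe of occurrence". The bands, introduced as an example, are the first 3 years from start of treatment, 3 to 5 years, and beyond 5 years. The overall adverse event tables in sections 9.7.2.5 and 9.7.2.6 give participants (number and share) and event counts, based on a Safety Population (section 9.7.1) that includes patients who entered after their first dose.

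**Bias.** The ENCePP checklist marks time-related bias (item 7.2.2) and measures of occurrence (item 3.3) as not applicable. Section 9.9 discusses missing data but not delayed entry.

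**The concern.** The clock for the bands starts at first dose, but the window in which an event can be recorded starts at consent. For a patient already on treatment at entry, the interval between the two belongs nominally to the early band and cannot yield a counted event.

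The mechanism differs by outcome. A child with an earlier neoplasia is largely kept out of the sample, by the exclusion criteria or because treatment has stopped. For those who do enrol, the time before consent is therefore mostly event-free by construction. A child with earlier hypoglycaemia can still enrol; the episode simply goes into medical history rather than incidence. Both push early-band incidence down.

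Neoplasia is the reason this registry exists (section 7.3), it is part of the primary endpoint (section 9.3.1.1), and its timing is a named secondary objective (section 8.2.2). Expansion to new countries is also what brings in patients already on treatment. An early rate that is too low beside a later rate that is nearly right would look like risk growing with exposure, and the Data Monitoring Committee and regulators would read it that way.

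**Working it through.** The protocol states no incidence, no sample size and no share of patients treated before entry, so there is no figure of its own to reproduce. What follows is illustrative.

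**Inputs.**
- Early band: 3 years from first dose (section 9.7.2.6, given as an example).
- f, the share of participants already on treatment at consent: assumed, 10% to 75%.
- t, years from first dose to consent for those participants: assumed, 1 to 3.

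**Step 1: constant rate, all time from first dose counted, no event counted before consent.**

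Observed / true early-band rate = 1 − f × t / 3

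| f | t (years) | Calculation | Observed / true |
|---|---|---|---|
| 10% | 1 | 1 − 0.10 × 1/3 | 0.97 |
| 25% | 1 | 1 − 0.25 × 1/3 | 0.92 |
| 50% | 1 | 1 − 0.50 × 1/3 | 0.83 |
| 50% | 2 | 1 − 0.50 × 2/3 | 0.67 |
| 50% | 3 | 1 − 0.50 × 3/3 | 0.50 |
| 75% | 2 | 1 − 0.75 × 2/3 | 0.50 |

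**Step 2: simulation for neoplasia.** Constant hazards of 0.002 and 0.01 per year were used, and already-treated patients whose event preceded consent were dropped from the sample. For (25%, 1 y), (50%, 1 y), (50%, 2 y) and (75%, 2 y), the rate with time counted from first dose was 0.91–0.92, 0.83, 0.67 and 0.50 of the truth. The crude proportion of participants gave practically the same ratios, so using proportions in place of rates does not avoid the problem. With risk time counted from the later of first dose and consent, the ratio was 0.99 to 1.00 throughout.

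**Step 3: the artificial trend.** If every delay is at most 3 years, the 3-to-5-year band is fully observed. Under a constant rate its ratio to the early band then appears as 1 / (1 − f × t / 3). For f = 50%, t = 2 that is 1 / 0.667 = 1.5, a rise of half where none exists.

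**Step 4: hypoglycaemia concentrated early.** Assume a rate three times as high in year 1, so relative yearly rates are 3, 1, 1 (total 5 over 3 years). For f = 50%, t = 1, counted events are 0.5 × 5 + 0.5 × 2 = 3.5.
- All time counted: 3.5 / 5 = 0.70 of the true rate.
- Delayed entry, one pooled band: observed time is 0.5 × 3 + 0.5 × 2 = 2.5 years; 3.5 / 2.5 = 1.40, against a true 5 / 3 = 1.67, a ratio of 0.84.

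| f, t | All time counted | Delayed entry, pooled band |
|---|---|---|
| 25%, 1 y | 0.85 | 0.93 |
| 50%, 1 y | 0.70 | 0.84 |
| 50%, 2 y | 0.60 | 0.90 |
| 75%, 2 y | 0.40 | 0.80 |

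Delayed entry thus removes the bias when the rate is steady within the band, but only part of it when events cluster soon after first dose.

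**The case against.** **The denominator is not stated.** Section 9.7.2.6 names no person-time and no risk set, gives the bands only as an example, and section 9.7.2.1 leaves detail to a statistical analysis plan that is not at hand. A reader might infer that the protocol already fixes a biased denominator. It does not, and the bias is conditional. What the protocol does fix is the entry rule, the capture window and the time origin. The only measure it states for the adverse event tables is participants in the whole Safety Population, and its checklist treats time-related bias as not applicable. Followed literally, that leads to the bias.

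**Retrospective collection may cover it.** The second sentence quoted from section 9.1 could be read as including adverse events, and section 11.1.1 ties the status of a newly detected condition to dosing rather than to study start. But section 9.1 does not mention adverse events, while sections 9.3.2.2 and 11.2.1 and Table 1 start their capture at enrolment or consent. The passages are unreconciled. Full retrospective capture could repair hypoglycaemia; it could not recover children with neoplasia who never entered.

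**Immortal time does not fit both outcomes.** Correct. Hypoglycaemia is not a stated exclusion, so that time is at risk but unobserved. Nor is neoplasia excluded uniformly: the stated US criterion concerns active or suspected disease, and US patients with a benign neoplasm may stay on treatment, so some can enrol with the event held as history.

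**The analysis is descriptive.** The banded analysis is secondary and carries no formal test. This limits the severity, but a description of when neoplasia occurs is itself an objective.

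**Conclusion.** The point holds in conditional form and should be fixed. If time before consent or all participants form the early-band denominator, first-3-year incidence of neoplasia and hypoglycaemia is understated, and a spurious increase with exposure can appear. The same gap affects the on-treatment incidence in the primary endpoint.

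Under a constant rate the understatement is about 3% for 10% already treated with a 1-year delay, and 50% for 75% with a 2-year delay. These are illustrations, not bounds. They rest wholly on assumed shares and delays, and on every child contributing the full band. A reader might take a large understatement as established; the documents do not support that, since they give neither quantity. They also do not support calling all of this immortal time: that describes neoplasia in the main, while for hypoglycaemia the fault is unobserved time at risk.

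**What to change.** 1. Reconcile section 9.1 with sections 9.3.2.2 and 11.2.1 and Table 1 on whether adverse events before consent are collected. If they are, flag them and present them apart from prospective incidence.
2. In sections 9.7.2.5 and 9.7.2.6, count risk time and events from the later of first dose and consent, each allocated to its true band since first dose.
3. Report neoplasia and hypoglycaemia separately for participants enrolled at or before first dose and for those already on treatment. This is needed because delayed entry in one pooled 3-year band does not fully correct events that cluster early, and because it assumes that patients already on treatment carry the same risk, at a given time since first dose, as new starters.
4. Add delayed entry, and the selection against earlier neoplasia, to the limitations in section 9.9.

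The date of first dose is already collected (section 9.3.2.4) and the consent date is required in source documents (section 9.8.3). Items 2 to 4 are therefore changes of analysis and reporting wording; item 1 clarifies the collection window. The price is wider intervals in the early bands, and small numbers in the group enrolled at first dose if most participants were already on treatment.
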